## **10.5 Post-Study Treatment**

After the end or early termination of the study treatment, the investigator may decide to further treat the patient according to clinical practice. Subsequent anticancer therapy should also be recorded.

#### 10.6 Treatment Accountability and Compliance

A pre-printed drug dispensing log and site drug accountability logs will be provided by the sponsor representative. Compliance with study treatment by the investigator is the responsibility of the investigator and is supervised by the sponsor representative through on-site monitoring visits. The investigator should maintain complete and accurate records of drug use data.

The person responsible for dispensing the drug recorded the use of all study drugs. Labels of MRG003 vials administered or dispensed to the patient must be complete (with the patient number and visit number, respectively). The production batch number and the expiry date of the investigational drug (MRG003 and sterile water for injection) must be recorded in the eCRF/drug accountability form, and the number of vials used and the administration date in each cycle must also be recorded (MRG003).

The person responsible for administration is responsible for recording the exact date and time that the patient was dosed. If there is an interruption in the infusion process, it should be recorded in the eCRF with the reason.

304	11	S	SA	VI	₹	ľ	7	7	4	SS	E	SS	M	B	N	Π

In this study, all subjects who received intravenous infusion of MRG003 were evaluated for drug toxicity throughout.

## 11.1 Definition of different types of adverse events

#### 11.1.1 Adverse Event Definitions

Definition of adverse event (AE): Any subject entering this trial after signing informed consent form develops or worsens any clinical condition, symptom, syndrome or disease affecting health during the clinical study, which is considered as an AE. Laboratory, vital sign, or ECG abnormalities were recorded as adverse events only if they were medically significant, i.e., symptomatic, requiring symptomatic treatment, leading to discontinuation, and/or fulfilling a seriousness criterion. An adverse event may be: a new disease; a worsening of symptoms or signs during treatment, or a worsening of a concomitant disease; an "adverse event" term does not imply a causal relationship to the trial drug.

In general, efficacy endpoints predefined in the protocol are not to be considered as AEs unless, due to the course, seriousness, or any other characteristics of such events, the investigator, in his/her opinion, considers these events to be exceptional in this medical setting, based on his/her best medical judgment.

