#### 6.3.4 Dose-limiting toxicity, maximum tolerated dose and recommended phase II dose

#### 6.3.4.1 Judgment criteria for dose limiting toxicity (DLT)

A DLT was defined as an AE (except allergic reaction) or abnormal laboratory value not related to disease progression, or concomitant disease, or concomitant medication, and met any of the following criteria in the DLT table (Table 4). Adverse events will be assessed according to CTCAE v4.03. Any subject who fails to complete the 21-day observation period for reasons other than DLT will be considered as not evaluable for DLT, and another subject in the same dose group should be added.

Table 4: Judgment criteria for DLT according to CTCAE 4.03 classification

Toxicity	Any of the following criteria
Blood	Grade 4 neutropenia lasting > 7 consecutive days
	Grade 3 thrombocytopenia lasting > 7 consecutive days
	Grade 4 thrombocytopenia
	Grade 3 febrile neutropenia (granulocytes < 1.0 × 109/L, body temperature ≥ 38.5°C) requiring antibiotics
Kidney	Serum creatinine greater than 3 times the upper limit of normal for > 7 consecutive days
	≥ Grade 3: Blood creatinine increased
Liver	Total bilirubin greater than 3 times the upper limit of normal for > 7 consecutive days
	≥ Grade 3 total bilirubin elevation
	Grade 3 AST or ALT elevation lasting > 7 consecutive days
	Grade 4 elevated aspartate aminotransferase (AST) or alanine aminotransferase (ALT)
Pancreas	Symptomatic amylase or lipase abnormalities ≥ CTCAE Grade 3
	Asymptomatic ≥ CTCAE Grade 3 amylase or lipase abnormality lasting longer than 7 days
Cardiovascular system	≥ Grade 3
Eye	≥ Grade 3
Skin	Grade 3 or 4 skin toxicities that remain uncontrolled despite symptomatic treatment
Nervous system	≥ Grade 3: Neurologic toxicity
Other Adverse Events	≥ Grade 3: Uncontrolled vomiting and nausea despite the use of antiemetic doses
	≥ Grade 3: Uncontrolled diarrhea despite the subject's use of antidiarrheal medication
	Treatment delay of > 14 days due to unresolved toxicity that does not resolve to Grade 1 or baseline
	Other ≥ Grade 3 AE

Any other unacceptable toxicity as determined jointly by the investigator and the sponsor's medical monitor

Note: 3 kinds of adverse reactions are not regarded as criteria for DLT judgment:  $\geq$  Grade 3 anemia (unless there is indirect relationship with MRG003);  $\geq$  Grade 3 lymphocytopenia (unless there is clinical significance);  $\geq$  Grade 3 hypercholesterolemia or hypertriglyceridemia.

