#### 8.1.6 Administration method and administration period

MRG003 will be administered as an intravenous infusion on Day 1 of each cycle.

Each MRG003 dosing cycle is every 3 weeks (Q3W). Each subject received up to 8 dosing cycles throughout the study.

Prior to the start of each dosing cycle, subjects must meet the following conditions to receive intravenous infusion of MRG003:

- Neutrophil count  $\geq 1.5 \times 10^9/L$  and platelet count  $\geq 75 \times 10^9/L$ . Supportive therapy was allowed to improve the subject's hematologic condition (except prior to the first dose).
- Adverse reactions related to study drug must have improved to baseline or CTCAE v4.03 grade ≤ 1. For adverse reactions that do not result in fatal organ damage, such as hair loss, the investigator may decide whether the drug can be administered to the subject.

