# 8.2 Dose Modifications, Modifications, and Delays

The investigator may delay the administration of study drug due to toxicity of study drug. Once a dose delay occurs, the scheduled time for subsequent doses should be adjusted later. However, if a subject delayed dosing for > 3 weeks (1 dosing cycle), the subject was considered withdrawn from the trial.

The investigator may also adjust the dose of study drug because of study drug toxicity, and a maximum of 2 dose reductions is allowed. However, patients in the initial dose 0.1 mg/kg group were not allowed to reduce the dose during the experiment, and patients in the second dose 0.3 mg/kg group were only allowed to reduce the dose once to 0.1 mg/kg during the experiment. If the subject is still intolerable after dose reduction for 2 times, the drug should be permanently discontinued and the patient should withdraw from the trial. If a subject's dose is reduced, subsequent doses will be adjusted according to the new dose, and re-escalation is not allowed.

Table 5: Dose Modification Table

Dose Level	MRG003 Dose
Dose Level	MRG003 Dose

	- 1	Previous Dose											
	- 2	First two doses											
•	If a subject	t delayed dosing for > 3 weeks, the subject was considered withdrawn ial											
•	If a subject required a dose reduction > -2 dose levels, the subject was permanently discontinued from the trial												

- A subject may require a dose reduction for any of the following adverse events:
  - For CTCAE v4.03 grade 3 to 4 non-hematologic adverse events related to drug toxicity that cannot be resolved to grade 2 or less within 72 hours after supportive care, study drug dose reduction is required. However, the investigator can determine to what extent the dose of the study drug can be not adjusted for adverse reactions that will not cause damage to vital organs, such as alopecia, which is recovered after supportive treatment;
  - Grade 4 neutropenia lasting > 5 days;
- Febrile neutropenia;

- Grade 4 thrombocytopenia;
- Grade 2 irreversible peripheral sensory nerve abnormalities; Grade 2 or higher neurological diseases, which still fail to return to the baseline level within 4 weeks after administration after supportive treatment;
  - Other adverse events decided by the investigator;

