#### **14.4.5 Safety Analysis Methods**

For safety analysis, descriptive statistics will be used to summarize incidence of adverse events (AEs) and calculate normal/abnormal changes of laboratory test results before and after treatment. The listing of various AEs and the listing of clinically significant abnormalities in laboratory parameters after treatment will be detailed.

Safety indicators will include adverse events, vital signs (blood pressure, pulse and body temperature) and laboratory data. Safety analysis will be based on Safety Analysis Set (SS).

The analysis of adverse events in the safety analysis only analyzed treatment-emergent adverse events (TEAEs). For adverse events (TEAEs) during the treatment period, all AEs occurred within 21 days after the last dose, and adverse events and serious adverse events were collected. Adverse events will be summarized, and the number and percentage of patients with adverse events and the number of events will be calculated, classified by MedDRA preferred term, and severity will be determined based on CTCAE v.4.03 grading. The list of adverse events will be listed according to the occurrence time of adverse events of subjects, the treatment period where they are located, and the CTCAE grade of adverse events.

Hematological toxicity was assessed with laboratory parameters. Neutropenia, thrombocytopenia, and anemia were graded by CTCAE and calculated according to the National Cancer Institute (NCI) Common Terminology Criteria. Qualitative and quantitative results of hematological toxicity will also be summarized.

The blood biochemical indicators of the subjects were assessed according to the blood biochemical reference values of the study hospital. Blood biochemical indicators were analyzed and summarized according to CTCAE grade.

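### The AE recording rule in Section 11.1.1 omits dose delay, dose reduction and DLT status, so some dose-changing or dose-limiting laboratory abnormalities need not be recorded as AEs

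*Protocol*

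**What the plan says.** **Recording rule.** Protocol Section 11.1.1 has laboratory, vital-sign and ECG abnormalities "recorded as adverse events only if they were medically significant, i.e., symptomatic, requiring symptomatic treatment, leading to discontinuation, and/or fulfilling a seriousness criterion". The words *only if* followed by *i.e.* make this a closed list of four triggers.

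**DLT definition.** Section 6.3.4.1 is wider: "A DLT was defined as an AE (except allergic reaction) or abnormal laboratory value not related to disease progression". Table 4 then has rows that rest on a laboratory value and a duration, such as "Grade 3 AST or ALT elevation lasting > 7 consecutive days", and one row that is symptom-free by its own terms: "Asymptomatic ≥ CTCAE Grade 3 amylase or lipase abnormality lasting longer than 7 days".

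**Dosing rules.** Section 8.1.6 sets neutrophil and platelet thresholds among the conditions before each cycle: "subjects must meet the following conditions to receive intravenous infusion of MRG003". Section 8.2 adds: "The investigator may delay the administration of study drug due to toxicity of study drug". It introduces its reduction triggers with "A subject may require a dose reduction for any of the following adverse events", and the list under that sentence includes Grade 4 neutropenia of more than 5 days and Grade 4 thrombocytopenia.

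**Analysis.** Section 14.4.5 states: "The analysis of adverse events in the safety analysis only analyzed treatment-emergent adverse events (TEAEs". The same section also grades haematology and biochemistry by CTCAE from the laboratory data and lists clinically significant laboratory abnormalities. Section 11.5.1 sets out what is collected for each AE, including relationship to study drug, whether the drug was stopped, action taken and outcome.

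**The concern.** Three parts of the protocol treat laboratory findings as toxicity that matters: the DLT table, the re-dosing conditions and the dose-reduction list. The rule that decides what becomes an AE refers to none of them. Section 8.2 calls certain laboratory findings adverse events, while 11.1.1 does not require them to be recorded as such.

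The type, severity, timing and relatedness of AEs is a secondary outcome in both Phase Ia and Phase Ib (Section 6.2.2). Low-grade AEs and AEs in later cycles also feed the choice of RP2D (Section 6.3.4.2). If a finding is never entered as an AE, the investigator's view of causality and the action taken are not collected with it, and no analysis plan can recover them afterwards. The AE tables could then show fewer toxicities than the DLT list and the dosing records imply.

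**Working it through.** The plan gives no figure on this point and no formula applies. The check sets the four triggers of 11.1.1 against each rule that acts on laboratory values.

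**Step 1: Table 4.** Criteria by row group: blood 4, kidney 2, liver 4, pancreas 2, cardiovascular 1, eye 1, skin 1, nervous system 1, other 5. Total: 4 + 2 + 4 + 2 + 1 + 1 + 1 + 1 + 5 = 21.

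Criteria that a laboratory value can meet alone, with or without a duration:
- blood 3 (Grade 4 neutropenia of more than 7 days; Grade 3 thrombocytopenia of more than 7 days; Grade 4 thrombocytopenia)
- kidney 2 (both creatinine rows)
- liver 4 (two bilirubin rows, two AST/ALT rows)
- pancreas 1 (the asymptomatic amylase/lipase row)

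Total: 3 + 2 + 4 + 1 = 10. None of the ten requires symptoms, symptomatic treatment, discontinuation or seriousness. The catch-all row for other AEs of Grade 3 or higher is worded through the AE definition; it is not among the ten and the point does not rest on it.

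**Step 2: Section 8.2.** Two named reduction triggers are laboratory-only: Grade 4 neutropenia of more than 5 days and Grade 4 thrombocytopenia. Neither requires an 11.1.1 trigger.

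**Step 3: Section 8.1.6.** Both count thresholds (neutrophils, platelets) can hold an infusion on the value alone. A delay of more than 3 weeks counts as withdrawal under 8.2 and would plausibly be caught as discontinuation. Shorter delays would not.

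**Step 4: three illustrative findings, each asymptomatic, untreated and non-serious.**

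| Finding | Rule that acts on it | Required AE under 11.1.1? | Where it still appears |
|---|---|---|---|
| Neutrophils below the threshold before Cycle 3, dose delayed by less than 3 weeks | 8.1.6, 8.2 | No | CTCAE laboratory summary, administration dates |
| Grade 4 thrombocytopenia in a later cycle, dose reduced | 8.2, which calls it an adverse event | No | CTCAE laboratory summary, dosing record |
| Grade 3 lipase for more than 7 days in Cycle 1 of Phase Ia | Table 4 | Not unless the DLT leads to discontinuation | DLT record, CTCAE laboratory summary |

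**Step 5: what is lost.** In each row the grade survives. Section 14.4.5 does not call for relationship, action taken or outcome in the laboratory summaries, and 11.5.1 collects those fields only for AEs. DLTs are observed and recorded in Cycle 1 only (Section 9.5), so the DLT record is no backstop for later cycles or for Phase Ib.

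**The case against.** The case on the other side is substantial.

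- **DLTs do not depend on AE status.** A reader might infer that laboratory DLTs drop out of the Phase Ia primary outcome. The protocol does not support that. Section 6.3.4.1 admits an abnormal laboratory value directly, Table 6 has its own line for documenting DLTs, and 14.4.3.1 analyses them separately. This stands in full for the ten laboratory-only rows.
- **A Cycle 1 DLT may already be a discontinuation.** Sections 6.2.2 and 9.5 say that dosing continues into Cycle 2 if there was no DLT. By implication a DLT stops treatment and meets a trigger. This is plausible but not stated, and it does not help with delays and reductions.
- **Section 8.2 calls its triggers adverse events,** so a site might record them on that basis. It might, but 8.2 governs dosing and 11.1.1 governs recording. Sites following different sections would record differently.
- **Other routes catch part of the rest.** These are symptomatic treatment, the seriousness category for medically important events (11.1.2, with an asymptomatic ALT example in 11.5.2) and the potential Hy's law report (11.5.3). They are partial and depend partly on judgement.
- **The data stay in the safety analysis.** Section 14.4.5 keeps the CTCAE grades, and Section 10.6 requires administration dates and vials used in each cycle, so delays and reductions can be traced. This stands. What is missing is the AE attributes, not the laboratory result.
- **Limiting laboratory AEs to medically significant ones is a coherent choice.** It is. The difficulty is that the definition of medically significant leaves out events on which the protocol itself acts.

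**Conclusion.** The point holds in a limited form. Section 11.1.1 is inconsistent with 6.3.4.1, 8.1.6 and 8.2. As written, an asymptomatic, untreated, non-serious laboratory abnormality that delays or reduces a dose, or is a DLT, need not be recorded as an AE. The consequence falls on the secondary AE outcome in both parts and on its agreement with the DLT and dose-modification records. It does not fall on the MTD decision through the ten laboratory-only rows.

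Three stronger readings should be avoided. Such an event is not barred from being an AE; it is only not required to be one. The count of 10 in 21 is of table rows, not of missed events, and Table 4 DLTs are assessed only in Cycle 1 of Phase Ia, so it does not mean that about half of DLTs go unrecorded. Nor is the toxicity hidden, since its grade is still summarised.

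The number of events affected cannot be estimated from the document. The conclusion assumes that the 11.1.1 list is closed, as its wording says, and that discontinuation does not include a temporary hold. If it did, some delays would be caught, but the text does not say so. Completion instructions outside the protocol might also narrow the gap; they are not available here. The change should be made because it is cheap and the lost fields cannot be rebuilt later, but the trial is not invalidated without it.

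**What to change.** Reconcile 11.1.1 with 6.3.4.1, 8.1.6 and 8.2 by adding to the list of triggers in 11.1.1: *leading to dose delay, interruption or reduction, or meeting a DLT criterion in Table 4*. Carry the same wording into the eCRF guidance so that sites record these events alike. This changes recording only; no dose, threshold, test or clinical rule is altered.

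The cost is one clause and the guidance text, slightly more AE entries, and a somewhat higher reported AE rate.

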# **6.5 Efficacy Assessments**

Response to tumor therapy will be assessed in this study using Response Evaluation Criteria in Solid Tumors RECIST v1.1, see Appendix II.

The primary outcome measure of Ib trial is objective response rate (ORR), the proportion of subjects with confirmed overall CR and confirmed overall PR in all subjects who have received the study drug.

Progression-free survival (PFS) for this study is defined as the time from the start of treatment with MRG003 until objective tumor progression or death from any cause. Duration of response (DOR) is defined as the time from the first documented response until disease progression or death among subjects with a confirmed objective response (CR or PR), with tumor evaluation according to RECIST v1.1 criteria. Overall survival (OS) is defined as the time from the start of treatment with MRG003 to death due to any cause.

For patients without disease progression after the last dosing cycle, tumor response should be assessed every 6 weeks and followed up for survival until disease progression or other anti-tumor treatment. Survival follow-up could be performed every 12 weeks after confirmation of disease progression or receipt of additional antineoplastic therapy. The follow-up period starts from the end of treatment cycle until death or study termination. During follow-up, survival status and subsequent tumor treatment need to be examined and recorded. Subsequent tumor treatment does not need to be recorded in electronic case report form (eCRF).

Tumor evaluation will be performed according to RECIST v1.1, and the results of imaging assessment methods should be recorded in the electronic case report form. During trial treatment, radiographic assessments may be performed  $\pm$  7 days from the scheduled date and the methodology should be consistent between baseline and subsequent follow-up. Whenever clinically permissible, the same oral or intravenous contrast agent was used for each scan, and, whenever possible, the same investigator/radiologist evaluated all patient scans during the study.

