#### 11.1.2 Definition of Serious Adverse Event

A serious adverse event (SAE) is an adverse event that, at any dose of study drug, results in:

- Means a patient died; or
- Life-threatening; or
- Required or prolonged hospitalization; or
- Results in persistent or significant disability or incapacity; or
- Results in congenital anomaly or birth defect;
- Other medically important event:

Note: The term "life-threatening" in the definition of "serious adverse event" refers to an event in which the patient is at immediate risk of death from the event; it does not refer to an event that hypothetically might have caused death if it were more severe.

Hospitalization or prolongation of hospitalization will not be considered an adverse event if the following conditions are met: hospitalization planned before enrollment in the study; a mobile hospitalization (12 hours); a hospitalization that is part of the normal treatment or monitoring of the disease under study but is not caused by a worsening of the disease; a hospitalization that is only related

to socioeconomic factors and not related to the disease (e.g., hospitalization for medical insurance reimbursement, accommodation problems or physical examination needs).

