#### 11.5.4 Serious Adverse Events Due to Disease Progression

Serious adverse events due to disease progression for all subjects treated with MRG003 should be reported according to the SAE reporting requirements within 21 days after signing the informed consent form at the first visit scheduled in the clinical trial protocol, throughout the study treatment period, and after the last dose of the study drug.

Serious adverse events due to disease progression that occur during the efficacy and survival follow-up periods of 21 months after the last dose of study drug do not need to be reported as SAEs.

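### Section 11.1.1 puts on-treatment progression deaths outside the AE definition by default, but 11.5.4 and 11.5.5 make them reportable, so whether they count as fatal SAEs/TEAEs depends on the section followed

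*Protocol*

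**What the plan says.** - **Section 11.1.1** ends the AE definition with an exemption: "In general, efficacy endpoints predefined in the protocol are not to be considered as AEs unless" the investigator, because of the course, seriousness or another feature of the event, "considers these events to be exceptional in this medical setting, based on his/her best medical judgment".
- **Section 6.5** defines the time-to-event endpoints. PFS runs from the start of treatment "until objective tumor progression or death from any cause". OS is "the time from the start of treatment with MRG003 to death due to any cause".
- **Section 11.1.2** builds the SAE on the AE: "A serious adverse event (SAE) is an adverse event that, at any dose of study drug, results in" one of a list of outcomes, the first of which is death.
- **Section 11.5.4** states: "Serious adverse events due to disease progression for all subjects treated with MRG003 should be reported according to the SAE reporting requirements". The period covers consent, treatment and 21 days after the last dose.
- **Section 11.5.5** requires any death in the window, expressly including death from tumor progression, to be reported within 24 hours whatever its relationship to the drug. For deaths in later follow-up, seriousness depends on a possible relationship to the drug. All deaths go into the death section of the eCRF.
- **Section 14.4.5** limits the adverse event analysis: "The analysis of adverse events in the safety analysis only analyzed treatment-emergent adverse events (TEAEs"), with a window that closes 21 days after the last dose.

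**The concern.** Two rules cover the same event and give different answers. Under 11.1.1, a death that is itself a predefined efficacy event enters the AE data only if an investigator judges it exceptional. Under 11.5.4 and 11.5.5, a progression death in the reporting window is reportable and no judgement of that kind is asked for.

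Safety is a secondary outcome in both parts, and the SAE and fatal-TEAE counts are among the figures that a first-in-human trial is read for. In open-label treatment of advanced cancer it is often hard to say whether a death came from the disease or the drug. A rule that lets such a death leave the AE tables on opinion makes the fatal-event count depend on attribution. In the multicentre Phase Ib part, two sites could classify the same kind of death differently and each be following the protocol. Section 7.6 also lists multiple serious adverse events as a ground for suspending the trial, so the classification matters beyond the tables.

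**Working it through.** The protocol gives no figure to reproduce. The check sets the sections side by side and follows one event through them.

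**Test event: a treated subject dies of tumor progression within 21 days of the last dose.**

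| Step | Following 11.1.1 | Following 11.5.4 / 11.5.5 |
|---|---|---|
| Predefined efficacy event? | Yes: death from any cause is a PFS and an OS event (6.5) | Not asked |
| Is it an AE? | No by default; yes only if judged exceptional | Treated as one: 11.5.4 applies the SAE reporting requirements |
| Is it an SAE? | No: an SAE must be an AE (11.1.2) | Yes; 11.5.5 applies a relationship test for seriousness only to later deaths, which implies that deaths inside the window are serious |
| Is it a fatal TEAE under 14.4.5? | No | Yes |

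**Do the windows overlap?** Section 11.5.4 runs to 21 days after the last dose, and so does the TEAE window in 14.4.5. The conflict therefore falls wholly inside the analysed period. The window wording in 11.5.5 is garbled (it ties 21 days to consent as well as to the last cycle); it is read here as the same window as 11.5.4.

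**Does the mention of seriousness in 11.1.1 reconcile the rules?** No. It is one of the features that may lead an investigator to call an event exceptional. Inclusion remains discretionary there and mandatory in 11.5.4.

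**Non-fatal serious complications of progression.** The efficacy endpoint is the progression finding, not the complication. The general definition in 11.1.1 counts worsening of symptoms or signs as an AE. Section 11.1.2 sets aside hospitalization for the disease under study only where worsening of that disease is not the cause, so hospitalization for worsening disease stays in. Both favour inclusion, although 11.1.1 does not say so outright.

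**Scale per reclassified death.** Inputs are the planned numbers in 7.1 and 14.1: 12 per Phase Ib cohort, 36 in Phase Ib, about 26 in Phase Ia. Assumption: the number treated equals the planned number. Shift in the fatal proportion = 1/n.

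- Phase Ib cohort: 1/12 = 0.083, or 8.3 percentage points.
- All Phase Ib: 1/36 = 0.028, or 2.8 points.
- Phase Ia: 1/26 = 0.038, or 3.8 points.

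The Phase Ib figures in the protocol are for evaluable subjects. If more are treated, each shift is slightly smaller.

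**The case against.** The strongest reply is that the rules address different things. Section 11.1.1 exempts endpoints (response, PFS, DOR, OS), while 11.5.4 deals with the clinical consequences of progression. A general default that itself allows exceptions would naturally yield to the specific rules in 11.5.4 and 11.5.5. Deaths are also collected in any case, because 11.5.5 puts every death into the eCRF death section.

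Much of this stands. A reader might infer that every serious event attributed to progression lacks a single definition. The documents do not support that for non-fatal events, where the general AE definition and the hospitalization wording in 11.1.2 point to inclusion. A reader might also infer that progression deaths would be lost; they would not. And it would be wrong to say that the safety analysis rests on adverse events alone, since 14.4.5 also covers vital signs and laboratory data.

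The reply does not dispose of fatal events. Death is at once the PFS/OS event and an SAE outcome, so the separation of endpoint from consequence breaks down there. No section says that the specific rule prevails. An entry in the death section does not make a death a fatal TEAE. An SAP could fix the tabulation, but the definition of an AE and what sites record as one belong to the protocol.

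**Conclusion.** The point holds for deaths. A progression death on treatment or within 21 days of the last dose is a non-AE by default under 11.1.1 and a reportable serious event under 11.5.4 and 11.5.5, and its place in the fatal SAE/TEAE count depends on which section is followed. For non-fatal serious complications the wording is ambiguous only.

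A reader might want to express this as a swing in SAE incidence. The documents give no count of SAEs or of progression-related events, so any such swing would rest on invented numbers. The supportable statement is the shift per death: 8.3, 2.8 or 3.8 points for denominators of 12, 36 and 26.

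Two limits apply. The Phase Ia primary outcome is not affected, because the DLT definition in 6.3.4.1 already excludes events related to disease progression. Differences between sites can arise only in Phase Ib, since Phase Ia has one centre; dependence on investigator opinion applies to both parts. The change is worth making because it corrects one stated rule that conflicts with another, at little cost.

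**What to change.** - **11.1.1:** limit the exemption to the RECIST finding of progression, that is, the endpoint itself. State that serious events and deaths in the collection window are recorded as AEs/SAEs whatever their attribution, with an eCRF flag for those due to progression.
- **11.5.4 and 11.5.5:** align both with that wording and give one common window. In the same edit, correct the exemption in 11.5.4, which refers to events in follow-up "of 21 months after the last dose of study drug do not need to be reported as SAEs", although the paragraph before it uses 21 days, and repair the window wording in 11.5.5.
- **14.4.5:** tabulate SAEs and fatal TEAEs for all events, and again excluding flagged ones. The second table still depends on investigator attribution, so the all-events table should be the main one.

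The cost is a few sentences, one eCRF flag and one extra table. The headline SAE rate may look less favourable.
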